4.6 Compliance and Drug Accountability

All quantities of the test articles must be reconciled at the completion of enrollment and a written explanation provided for any discrepancies. Unless specific written instructions to the contrary are provided by Novavax, all unused test articles are to be inventoried, and either

destroyed or returned to Novavax (or designee) by the clinical site upon notice by Novavax or the site monitor. All used vials will be accounted for on the clinical site's IP Dispensation Log by applying the tear-off portion of the vial/syringe label.

5 SELECTION OF TRIAL SUBJECTS

5.1 Inclusion Criteria

Subjects must meet all of the following criteria to be eligible to participate:

- 1) Clinically-stable adult male or female, ≥ 65 years of age. Subjects may have 1 or more chronic medical diagnoses, but should be clinically stable as assessed by:
 - Ambulatory status, living independently in the community or in a residential facility providing minimal assistance (eg, meal preparation and transport),
 - Absence of changes in medical therapy within 1 month due to treatment failure or toxicity,
 - Absence of medical events qualifying as serious adverse events within the prior 2 months, and
 - Absence of known, current, and life-limiting diagnoses which render survival to completion of the protocol unlikely in the opinion of the investigator.
- 2) Willing and able to give informed consent prior to trial enrollment, and
- 3) Living in the community and able to attend trial visits, comply with trial requirements, and provide timely, reliable, and complete reports of adverse events.

5.2 Exclusion Criteria

Subjects will be excluded if they meet any of the following criteria:

- 1) Participation in research involving investigational product (drug / biologic / device) within 45 days before planned date of study vaccination.
- 2) Participation in any previous Novavax's influenza vaccine clinical trial(s).
- 3) History of a serious reaction to prior influenza vaccination, known allergy to constituents of Fluzone Quadrivalent or polysorbate 80.
- 4) History of Guillain-Barré Syndrome (GBS) within 6 weeks following a previous influenza vaccine.
- 5) Received any vaccine in the 4 weeks preceding the trial vaccination and any influenza vaccine within 6 months preceding the trial vaccination.
- 6) Any known or suspected immunosuppressive illness, congenital or acquired, based on medical history and/or physical examination.
- 7) Chronic administration (defined as more than 14 continuous days) of immunosuppressants or other immune-modifying drugs within 6 months prior to the administration of the trial vaccine. An immunosuppressant dose of glucocorticoid will be defined as a systemic dose ≥ 10 mg of prednisone per day or equivalent. The use of topical, inhaled, and nasal glucocorticoids will be permitted.

Nanoparticle Influenza	Vaccine, Quadrivalent	Confidential	qNIV-E-301 Protocol
Novavax, Inc.	Version 4	4.0 – 31 October 2019	Page 40

- 8) Administration of immunoglobulins and/or any blood products within the 3 months preceding the administration of the trial vaccine.
- 9) Acute disease at the time of enrollment (defined as the presence of a moderate or severe illness with or without fever, or an oral temperature ≥ 38.0°C, on the planned day of vaccine administration).
- 10) Any condition that in the opinion of the investigator would pose a health risk to the subject if enrolled or could interfere with evaluation of the vaccine or interpretation of trial results (including neurologic or psychiatric conditions deemed likely to impair the quality of safety reporting).
- 11) Known disturbance of coagulation.
- 12) Suspicion or recent history (within 1 year of planned vaccination) of alcohol or other substance abuse.

6 TRIAL ASSESSMENTS AND PROCEDURES

A trial schematic flowchart is provided in Appendix 1. A detailed description of procedures performed at each visit is provided in Section 6.1.

6.1 Trial Visit Procedures

6.1.1 Day 0 – Screening Visit

The following procedures will be performed on the day of the planned vaccination:

- Written informed consent will be obtained in conformance with Section 11.3 of this protocol.
- Inclusion and exclusion criteria review consistent with Section 5.
- Review of medical history, including influenza vaccination history in the previous 3 years (with emphasis on 2018-19 vaccine) and history of adverse reactions to prior influenza vaccines and allergies.
- Medication history, including concomitant medications and vaccines within the last year.
- Physical examination including the head, eyes, ears, nose, and throat (HEENT), abdomen, extremities, and at least inguinal, cervical, and axillary nodes, gross motor function, and skin; vital signs (heart rate, blood pressure, respiratory rate, and oral temperature); height and weight.

Note that further procedures may be performed at the investigator's discretion in order to adequately screen subjects against eligibility criteria and/or to confirm medical history. Potential subjects who meet all of the inclusion criteria and none of the exclusion criteria may be enrolled. *Note: Subjects should be free of acute illness (defined as the presence of a moderate or severe illness with or without fever, or an oral temperature* $\geq 38.0^{\circ}$ C) *in order to receive the test article injection. Subjects presenting with an acute illness on Day 0 may return to the trial site within the next 7 days, as the enrollment timelines allow, to receive their injection provided symptoms have resolved.*

6.1.2 Day 0 – Injection Visit

All subjects with confirmed eligibility will have the following procedures performed:

- Blood draw for baseline immunogenicity testing (20 mL, see Section 7.1).
- A subset of approximately 140 subjects from several pre-designated clinical sites (to target approximately 70 evaluable subjects per treatment group) will provide additional blood samples (27 mL per visit) at 4 time points (ie, Days 0, 7, 28, and 182) to support testing of cell-mediated immune responses (CMI). Note: All subjects at several pre-designated CMI testing sites will participate in CMI blood sampling and the Informed Consent document at those sites will be adjusted accordingly.
- Randomization to a treatment group.
- Alcohol swab cleansing of the injection site followed by IM injection of the assigned trial treatment into the deltoid muscle of the non-dominant arm. *Note: If the non-dominant arm*

is not available for the injection due to post-surgical changes, skin changes, or prior injury, the dominant arm may be used.

- Monitoring for any AEs for approximately 30 60 minutes following vaccination.
- Post-injection vital sign collection (heart rate, blood pressure, respiratory rate, and oral temperature) at 30 60 minutes following vaccination.
- Distribution of the subject diary, thermometer, and a measuring tool to facilitate documentation of any AEs (solicited and unsolicited), concomitant medications, physicians visits, or hospitalizations, occurring from the time of discharge from the trial clinic on Day 0 through Day 6 (inclusive). Subjects will also be instructed to call the trial clinic for any Grade 3 (severe) solicited or unsolicited health events, and/or health status changes of concern to the subject.
- Schedule the Day 7 or 28 visit before subjects may be dismissed from the clinic.

6.1.3 Day 3 (± 1 day) – Safety Telephone Contact

• Using an IRB-approved script, the trial staff will contact the subjects using a telephone call to query for any Grade 3 solicited or unsolicited event and/or SAE experienced, and any concomitant medications taken for these events since the last visit. Subjects may be asked to return to the clinic for an unscheduled visit to evaluate the event(s) at the trial investigator's discretion.

6.1.4 Day 7 (± 1 day) – Follow-up Visit

A subset of approximately 140 subjects who were enrolled at several pre-designated clinical sites, and who provided blood for CMI responses at Day 0, will return to the clinic on Day 7 for the following procedures:

- Vital sign collection (heart rate, blood pressure, respiratory rate, and oral temperature).
- Interval history to query for any unsolicited AEs, including MAEs, SNMCs, or SAEs, occurring since the last trial visit, and any concomitant medications taken. A directed physical examination may be performed at the investigator's discretion to evaluate any AEs.
- Blood draw to assess CMI responses (27 mL).
- Schedule the Day 28 visit.

6.1.5 Day 28 (± 4 days) – Follow-up Visit

All subjects will return to the clinic on approximately Day 28 for the following procedures:

- Vital sign collection (heart rate, blood pressure, respiratory rate, and oral temperature).
- Review and collection of subject diary.
- Blood draw for immunogenicity assessments (20 mL) for all subjects.
- Blood draw to assess CMI responses (27 mL) for a subset of approximately 140 subjects who were enrolled at several pre-designated clinical sites.

- Interval history to query for any unsolicited AEs, including MAEs, SNMCs, or SAEs, occurring since the last trial visit, and any concomitant medications taken. A directed physical examination may be performed at the investigator's discretion to evaluate any AEs.
- Schedule the Day 90 telephone contact and the Day 182 in-clinic visit.

6.1.6 Day 90 (± 7 days) – Safety Telephone Contact

• Using an IRB-approved script, the trial staff will contact the subjects using a telephone call to query for any MAEs, SAEs, and SNMCs since their last visit, and any concomitant medications taken for these events.

6.1.7 Day 182 (± 7 days) – Follow-up Visit

At Day 182, all subjects will return to the clinic for the following procedures:

- Vital sign collection (heart rate, blood pressure, respiratory rate, and oral temperature).
- Blood draw for immunogenicity assessments (20 mL) for all subjects.
- Blood draw to assess CMI responses (27 mL) for a subset of approximately 140 subjects who were enrolled at several pre-designated clinical sites.
- Interval history to query for any MAEs, SNMCs, or SAEs occurring since the last telephone contact, and any concomitant medications taken for these events. A directed physical examination may be performed at the investigator's discretion to evaluate any AEs.
- Schedule the end of the trial (Day 364) telephone contact.

6.1.8 Day 364 (± 14 days) – Safety Telephone Contact

- Using an IRB-approved script, the trial staff will contact the subjects using a telephone call to query for any MAEs, SAEs, and SNMCs since their last visit, and any concomitant medications taken for these events.
- This visit will mark the end of the trial for the subjects.

6.2 Unscheduled Visits

Unscheduled visits are defined as any visits performed to the site outside of the regular visit schedule and can occur at the investigator's discretion for any other trial procedures deemed necessary. Subjects will be encouraged to notify the investigator if any severe (Grade 3) local or systemic solicited AEs occur within the 7-day post-dosing period (eg, from Day 0 through Day 6), or if any severe, serious, or otherwise concerning AEs occur at any time following dosing. If symptoms are presented that would require a physical exam to adequately assess potential AEs, the exam should be performed and vital signs collected.

6.3 Concomitant Therapy

Subjects may receive all concomitant medications and procedures deemed necessary to provide adequate healthcare during the trial, with the exception of those specified in the exclusion criteria. Routine medical standards of care are permitted, including vaccines needed for emergent indications (eg, tetanus booster in response to a penetrating injury). Routine (ie, non-emergent) vaccinations, except the seasonal influenza vaccine, are permitted for all

subjects after completion of the Day 28 trial visit. Subjects who receive a seasonal influenza vaccine outside of the study before Day 364 will be considered protocol deviations.

Concomitant medications, procedures, and hospitalizations will be recorded throughout the trial including the period from the day informed consent is obtained through the end of trial follow-up. All new or changed concomitant medications taken through Day 28 will be recorded; thereafter, only concomitant medications taken for MAEs, SNMCs, or SAEs will be recorded. The investigator will document the reason for use of the concomitant medication.

6.4 Declining Trial Treatments or Procedures

Subjects have the right to decline trial treatment or other trial procedures for any reason at any time during the trial. This trial contemplates one injection of either Quad-NIV with Matrix-M1 adjuvant or Fluzone Quadrivalent. Refusal of the investigational test article on Day 0 constitutes trial withdrawal without exposure, and no further follow-up is required. If a subject declines trial procedures subsequent to receipt of the investigational product, it should be recorded as a protocol deviation and the reason should be clearly documented in the source document. The subject will be asked to complete all other trial procedures as applicable. If the subject does not wish to remain in the trial, the subject can choose to withdraw consent and discontinue at any time as outlined in Section 6.5.

The investigator may, at his/her discretion, restrict a subject from receiving trial treatment or other trial procedures if he/she considers it to be in the subject's best interest to do so, but can suggest that the subject remain in the trial to be followed for safety if the subject has received a test article. In this situation, the reason for not performing the trial treatment and/or procedure should also be recorded as a protocol deviation and clearly documented in the source document.

6.5 Premature Discontinuation from Trial

Subjects who provide consent but are found to be ineligible on screening will be informed of the reason for ineligibility and may be provided with local medical referral by the investigator as appropriate, but will receive no further trial follow-up.

Subject participation in the trial is strictly voluntary. Subjects have the right to withdraw from the trial at any time and for any reason, without penalty. The investigator may also, at his/her discretion, discontinue subjects from the trial if he/she considers it to be in the participant's best interest to do so, or if the subject is not willing or able to comply with the trial requirements. Novavax will be notified immediately by the investigator if a subject prematurely ends trial participation. The reason for early discontinuation will be clearly documented in the electronic case report form (eCRF). A withdrawal due to an AE will initiate additional reporting requirements as outlined in Section 8.3.

In the event of early termination, investigators will make every reasonable effort to perform trial completion procedures. Trial completion procedures will include a query for any MAEs, SNMCs, or SAEs occurring since the last trial visit, and any concomitant medications taken to treat these events. If the subject discontinues from the trial prior to the Day 28 visit, sites will

Nanoparticle Influenza	Vaccine, Quadrivalent	Confidential	qNIV-E-301 Protocol
Novavax, Inc.	Version 4	.0 – 31 October 2019	Page 45

request the subjects to provide blood samples for serology testing (20 mL). Subjects that terminate from the trial early will not be replaced.

6.6 **Protocol Deviations**

A protocol deviation (PD) will be defined as a failure to comply with the requirements set forth in the protocol. PDs may be determined programmatically through the course of the trial. Examples of programmatically-determined PDs are provided in Table 2.

Missed Visit
Out of Window Visit
Trial Procedure Not Done
Randomization Error

Table 2: Programmatically-Determined Protocol Deviations

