3.2 Trial Endpoints

3.2.1 Primary Endpoints

- Comparative HAI antibody responses (assayed with egg-propagated virus) on Day 28, summarized in terms of the ratio of geometric mean titers (GMTs) AND seroconversion rate (SCR) difference, between subjects receiving Quad-NIV or Fluzone Quadrivalent for all 4 vaccine homologous influenza strains (ie, 2 influenza A and 2 influenza B strains). Non-inferiority for each homologous strain will be demonstrated if:
 - The lower bound of the two-sided 95% CI on the ratio of the GMTs $(GMT_{QuadNIV}/GMT_{Fluzone})$ is ≥ 0.67 ,

AND

• The lower bound of the two-sided 95% CI on the difference between the SCRs $(SCR_{QuadNIV}-SCR_{Fluzone})$ is $\geq -10\%$.

Nanoparticle Influenza	Vaccine, Quadrivalent	Confidential	qNIV-E-301 Protocol
Novavax, Inc.	Version 4	4.0 – 31 October 2019	Page 33

• Number and percentage (95% CI) of subjects with solicited local and systemic adverse events over the 7 days post-injection (ie, Day 0 through Day 6, inclusive); all adverse events through 28 days post-injection (ie, Day 0 through Day 27, inclusive); and MAEs, SAEs, and SNMCs – including AESIs – through 1 year post-injection.

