8 TRIAL ASSESSMENT OF SAFETY

8.1 Adverse Events

Adverse events (AEs) are defined as any unfavorable or unintended change in the physical, psychological, or biochemical condition of the subject. An AE temporally related to participation in the trial or due to a procedure performed in the trial, will be documented whether or not considered related to the test article. This definition includes intercurrent illnesses and injuries, and exacerbations of pre-existing conditions. Stable pre-existing conditions which do not change in nature or severity during the trial are not considered AEs; however, these should be collected as part of the medical history. AEs will be considered treatment emergent from the date and time of the first administration of the investigational product.

Data concerning all classes of adverse events will be collected at scheduled visits from the time informed consent is obtained on Day 0 through Day 28, inclusive. After these specified days, data concerning MAEs, SNMCs, and SAEs will be collected (see Sections 8.1.4 and 8.2 for details of these AEs), as well as additional information regarding outcomes/resolutions of AEs reported prior that had no stop date recorded. In addition to the scheduled visits, subjects will be instructed to notify the investigator and/or return to the clinic if any severe AE (solicited or otherwise) or event fulfilling the definition of an SAE occurs at any time following vaccination. If at a scheduled or unscheduled visit, symptoms are presented that would require a physical exam to adequately assess potential AEs, the exam should be performed and vital signs collected. Adverse events will be recorded as observed by the investigator, designated personnel, or as provided by the subject on the diary card or during the in-person visit. Full details of the AE (ie, nature, date of onset, and recovery, as well as an assessment of severity, relationship to trial treatment [unsolicited events only], seriousness, treatment, and outcome) will be recorded in the source documentation and captured in the eCRF, and will generally require the investigator(s) causality assessment, except as discussed below.

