APPENDIX 1 – QNIV-E-301 TRIAL PROCEDURES SCHEDULE

Note: Procedures shaded in grey are performed via scripted telephone call. ^[1] Vital signs to be captured pre-vaccination and between 30 to 60 minutes post-vaccination.

^[2] All adverse events and concomitant medications taken will be collected through Day 28; thereafter, only MAEs, SAEs, and SNMCs and medications taken for these events will be collected.

^[3] The subject diary will be reviewed by the investigator and collected at the Day 28 visit.

^[4] If needed, a physical examination may be performed, based on the investigator's discretion.

^[5] To be collected from a subset of approximately 140 subjects from several pre-designated clinical sites.

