8.1.2 Unsolicited Adverse Events

Unsolicited adverse events are defined as any adverse events occurring within the 7-day window following vaccination and not specifically solicited in the diary, or any adverse event that occurs outside the 7-day diary solicitation period. The number (percentage) of subjects with unsolicited AEs will be summarized by Medical Dictionary for Regulatory Activities (MedDRA) coded by system organ class (SOC) and preferred term (PT). All unsolicited AEs will be assessed for severity (Section 8.4 in Protocol) and for causality (Section 8.5 in Protocol).

The following summaries of unsolicited AEs will be presented for all subjects in the Safety Population as part of the primary analysis of safety:

- Overall summary of unsolicited AEs by treatment group (Days 0 28).
- A summary by severity (normal, mild, moderate, or severe), MedDRA SOC, PT, and treatment group (Days 0 28).
- A summary by relationship (causality) to test article of an AE (unlikely/unrelated, possibly, probably, or definitely) to test article, MedDRA SOC, PT, and treatment group (Days 0 28).

- A summary of severe and related (unlikely/unrelated, possibly, probably, or definitely) AEs, MedDRA SOC, PT, and treatment group (Days 0 28).
- A summary of any AEs including MAEs, SNMCs and SAEs, by MedDRA SOC, PT, and treatment group (Days 0 28).

The final analysis will include the following summaries of unsolicited AEs.

- Overall summary of unsolicited AEs by treatment group (Days 0 364).
- A summary by severity (normal, mild, moderate, or severe), MedDRA SOC, PT, and treatment group (Days 0 364).
- A summary by relationship (causality) to test article of an AE (unlikely/unrelated, possibly, probably, or definitely) to test article, MedDRA SOC, PT, and treatment group (Days 0 364).
- A summary of severe and related (unlikely/unrelated, possibly, probably, or definitely) AEs, MedDRA SOC, PT, and treatment group (Days 0 364).
- A summary of any AEs including MAEs, SNMCs and SAEs, by MedDRA SOC, PT, and treatment group (Days 0 364).

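### The primary all-AE window is Day 0-27, but collection and SAP tables run to Day 28, and Protocol 6.5 names no all-AE query or diary retrieval for subjects leaving before Day 28

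*Protocol*

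**What the plan says.** **Endpoint.** Protocol 3.2.1, the synopsis and SAP 2.2.1 define the primary all-AE endpoint as "all adverse events through 28 days post-injection (ie, Day 0 through Day 27, inclusive").

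**Collection.** Protocol 8.1 collects all classes of AE "from the time informed consent is obtained on Day 0 through Day 28, inclusive". Footnote 2 of the procedures schedule (Protocol Appendix 1, repeated in the SAP) reads "All adverse events and concomitant medications taken will be collected through Day 28; thereafter, only MAEs, SAEs, and SNMCs".

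**Tables.** SAP 8.1.2 lists "Overall summary of unsolicited AEs by treatment group (Days 0 28"), where the dash between 0 and 28 was lost in text extraction. The other unsolicited-AE tables for the primary safety analysis carry the same window. SAP 8.2 also runs the unblinded-review summary of MAEs and SNMCs to Day 28. That does not conflict with their own endpoint, which runs to one year.

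**Scheduled queries.**
- Day 3 call (Protocol 6.1.3): Grade 3 events and SAEs only.
- Day 7 visit (6.1.4): all unsolicited AEs, but only in the cell-mediated-immunity subset of about 140 of 2650 subjects.
- Day 28 visit, headed "6.1.5 Day 28 (± 4 days) – Follow-up Visit": "Interval history to query for any unsolicited AEs, including MAEs, SNMCs, or SAEs". The diary is reviewed and collected here.
- Day 90 call (6.1.6): "to query for any MAEs, SAEs, and SNMCs since their last visit".
- Early termination at any time (6.5): "Trial completion procedures will include a query for any MAEs, SNMCs, or SAEs occurring since the last trial visit". Before the Day 28 visit, a serology sample is also requested.

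**The concern.** Describing the safety profile, including the 28-day all-AE profile, is a primary objective. A subject who leaves before Day 28 stays in the Safety Population, and SAP 12.5 makes no general substitution for missing data, so an AE that was never elicited is tabulated as no AE. The authors of 6.5 did consider these leavers, since they added a blood draw, yet the named AE query is the one suited to later follow-up. The diary is exposed too: its only scheduled collection is the visit these subjects do not attend, so solicited reactogenicity could be incomplete as well.

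Two further gaps sit beside this one. The Day 28 visit may fall on Day 24, before the endpoint window closes, and no later contact asks about all AEs. Programmers also face two windows within one SAP, Day 0-27 in Section 2.2.1 and Days 0-28 in Section 8.1.2.

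**Working it through.** **1. Window length.** Day 0 through Day 27 is 28 calendar days, which reproduces the stated 28 days. Day 0 through Day 28 is 29 days, longer by 1/28 = 3.6%.

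**2. Endpoint days after an early visit.** The visit window is 28 ± 4, that is Days 24-32. Treat the visit day itself as covered and count the days after it up to Day 27.

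**3. Event rate (an assumption).** Protocol 1.6.1.1 gives Phase 2 rates through Day 28 for the chosen formulation: unsolicited AEs 18%, MAEs 7%. MAEs are still queried at Day 90, so the exposed part is the subjects with only non-attended AEs. Taking MAEs as a subset of unsolicited AEs, this is 18% − 7% = 11%. The high-dose comparator gives the same figure, 20% − 9% = 11%.

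With constant hazard, h = −ln(1 − 0.11)/28 = 0.00416 per day. The risk missed when the last L days are not queried is exp(−h(28 − L)) − exp(−28h).

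| Visit day | Unqueried endpoint days L | Share of window | Risk missed (points) |
|---|---|---|---|
| 24 | 3 | 10.7% | 1.12 |
| 25 | 2 | 7.1% | 0.74 |
| 26 | 1 | 3.6% | 0.37 |
| 27-32 | 0 | 0 | 0 |

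With visits spread evenly over the nine days, the mean is (1.12 + 0.74 + 0.37)/9 = 0.25 points.

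**4. The extra day in the tables.** The added risk is exp(−28h) − exp(−29h). At the 11% rate this is 0.37 points, about 5 subjects per arm of 1325. At the full 18% rate, h = −ln(0.82)/28 = 0.00709 and the addition is 0.58 points. It applies to subjects whose Day 28 is actually covered by a query.

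**5. Leavers before Day 28.** The documents give no expected number. If a fraction d of an arm leaves before Day 28 and every non-attended AE in them is missed, the arm-level loss is at most d × 11%:
- d = 1%: 0.11 points, about 1.5 subjects of 1325.
- d = 10%: 1.1 points, about 14.6 subjects.

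The 10% is the whole planned per-protocol attrition (Protocol 10.5), which covers more than early withdrawal, so the second figure is a ceiling.

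**The case against.** The best defence is that the plan catches most of what matters by other routes.
- SAP 12.4 encourages a dosed subject who withdraws to return for the scheduled safety assessments, and the schedule includes all-AE review at Day 28.
- The wording of 6.5 is not exclusive, and the requested blood sample implies a contact at which AEs could be raised.
- A withdrawal of consent because of an AE must reach the Medical Monitor within 24 hours (Protocol 8.3), and the reason for discontinuation goes in the eCRF.
- The diary records solicited and unsolicited events on Days 0-6 (8.1.1).
- Subjects are told to report severe, serious or otherwise concerning events (6.1.2, 6.2, 8.1).
- Safety analysis is descriptive, with no test or margin, and the visit window and table window are the same in both arms.

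Most of this stands, and it rules out several stronger readings that a reader might infer:
- *AEs in early leavers are never asked about.* Not supported: SAP 12.4 and the reporting routes above exist. The accurate statement is that no scheduled query is named.
- *Events that drove the subject out are lost.* Not supported, given the 24-hour report and the recorded reason.
- *A Day 24 visit costs 2.4-2.6 points.* That requires four lost days at the full 18-20% rate. The count is three days, and MAEs are still asked about at Day 90.
- *Everyone not seen early is over-counted by a day.* A subject seen on Day 27 loses no endpoint day, but has no scheduled all-AE query covering Day 28 either.
- *The loss differs by arm.* This is possible if early leaving differs, but the documents give no figure for it.

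What the defence does not remove: encouragement to return does not reach a subject who has gone for good, no text tells the site to retrieve that subject's diary, and nothing reconciles Day 27 with Day 28.

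**Conclusion.** The point holds as a misalignment that should be corrected, with a small expected effect. Two parts are plain on the page: the endpoint and the tables use different windows, and the termination query in 6.5 does not match the all-AE collection period. The third, early Day 28 visits, follows from the visit window combined with the Day 90 script. The collection footnote nominally covers those days, but no contact is scheduled to do it.

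The events without a scheduled query are mainly non-severe, non-attended AEs, together with unretrieved diary data. Each of the three effects is about 1 point or less at arm level, even at the ceiling for leavers. All the sizes depend on the Phase 2 rates carrying over, on MAEs being a subset of unsolicited AEs, and on constant hazard. The averages also depend on the unknown spread of visit days and number of leavers. SAE, MAE, SNMC and immunogenicity results are untouched.

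**What to change.** (a) **Protocol 6.5.** For discontinuation before the Day 28 visit, query all AEs since the last contact and retrieve the diary. Keep the MAE/SNMC/SAE query for later discontinuation. The cost is two lines of text and no new visit or sample. If Day 28 visits are already complete, report the number of earlier leavers by arm instead.

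(b) **SAP 8.1.2.** Cut the primary-endpoint AE tables at onset Day 0-27, as in SAP 2.2.1. Alternatively, choose one window and use it in the endpoint, the collection text and the tables. The cost is a date cut in the programs, or wording changes if Day 28 is chosen.

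(c) **Early Day 28 visits.** Report by arm how many subjects had the visit before Day 27, as a stated limit on ascertainment. The cost is one line in a table. Do not add a question on minor AEs to the Day 90 call: it would rely on about two months' recall, in early-visit subjects only, and would make ascertainment unequal.
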